7.4.2.2 Management of Drug-related Infusion Reactions in Parts 1A and 1B

Since nivolumab and BMS-986315 contain only human immunoglobulin protein sequences, they are unlikely to be immunogenic and induce infusion or hypersensitivity reactions. However, if such a reaction were to occur, it might manifest with fever, chills, rigors, headache, rash, pruritus, arthralgias, hypotension, hypertension, bronchospasm, or other allergic-like reactions. All Grade 3 or 4 infusion reactions should be reported within 24 hours to the study medical monitor and reported as an SAE if it meets the criteria. Infusion reactions should be graded according to NCI CTCAE (Version 5.0) guidelines.

Treatment recommendations are provided below and may be modified based on local treatment standards and guidelines, as appropriate:

For Grade 1 symptoms (mild reaction; infusion interruption not indicated; intervention not indicated):

- Remain at bedside and monitor participant until recovery from symptoms. The following prophylactic premedications are recommended for future infusions: diphenhydramine 50 mg (or equivalent) and/or acetaminophen/paracetamol 325 to 1000 mg at least 30 minutes before additional nivolumab or BMS-986315 administrations.

For Grade 2 symptoms: (moderate reaction required therapy or infusion interruption but responds promptly to symptomatic treatment (eg, antihistamines, non-steroidal antiinflammatory drugs, narcotics, corticosteroids, bronchodilators, IV fluids); prophylactic medications indicated for ≤ 24 hours):

- Stop the study drug infusion, begin an IV infusion of normal saline, and treat the participant with diphenhydramine 50 mg IV (or equivalent) and/or acetaminophen/paracetamol 325 to 1000 mg; remain at bedside and monitor participant until resolution of symptoms. Corticosteroid and/or bronchodilator therapy may also be administered as appropriate. If the infusion is interrupted, then restart the infusion at 50% of the original infusion rate when symptoms resolve; if no further complications ensue after 30 minutes, the rate may be increased to 100% of the original infusion rate. Monitor participant closely. If symptoms recur, then no further study medication will be administered at that visit.

For future infusions, the following prophylactic premedications are recommended: diphenhydramine 50 mg (or equivalent) and/or acetaminophen/paracetamol 325 to 1000 mg should be administered at least 30 minutes before nivolumab and/or BMS-986315 infusions. If necessary, corticosteroids (up to 25 mg of hydrocortisone or equivalent) may be used.

For Grade 3 or 4 symptoms: (severe reaction, Grade 3: prolonged [ie, not rapidly responsive to symptomatic medication and/or brief interruption of infusion]; recurrence of symptoms following initial improvement; hospitalization indicated for other clinical sequelae [e.g., renal impairment, pulmonary infiltrates]; Grade 4: Life-threatening; pressor or ventilatory support indicated):

- Immediately discontinue infusion of study drug. Begin an IV infusion of normal saline and treat the participant as follows: recommend bronchodilators, epinephrine 0.2 to 1 mg of a 1:1000 solution for subcutaneous administration or 0.1 to 0.25 mg of a 1:10,000 solution injected slowly for IV administration, and/or diphenhydramine 50 mg IV with methylprednisolone 100 mg IV (or equivalent), as needed. Participant should be monitored until the Investigator is comfortable that the symptoms will not recur. Study drug will be permanently discontinued except for a Grade 3 infusion reaction that returns to Grade 1 in less than 6 hours. Investigators should follow their institutional guidelines for the treatment of anaphylaxis. Remain at bedside and monitor participant until recovery of the symptoms.
- In case of late-occurring hypersensitivity symptoms (e.g., appearance of a localized or generalized pruritus within 1 week after treatment), symptomatic treatment may be given (e.g., oral antihistamine or corticosteroids).

7.4.2.3 *Prevention and Management of Drug-related Infusion Reactions in Part 1C*

Cetuximab is known to cause serious and fatal infusion reactions. Among 1373 patients who received cetuximab across clinical trials, any grade infusion-related reactions (IRR) occurred in 8.4% and Grade 3/4 in 2.2% of patients.²² IRRs might manifest with fever, chills, rigors, headache, rash, pruritus, arthralgia, hypotension, hypertension, bronchospasm, rapid onset of airway obstruction, shock, loss of consciousness, myocardial infarctions and/or cardiac arrest. Approximately 90% of severe IRR to cetuximab occur in the first infusion despite premedication with antihistamines. Infusions should be performed in a setting with resuscitation equipment and other agents necessary to treat anaphylaxis.

All Grade 3 or 4 infusion reactions should be reported within 24 hours to the study medical monitor or designee and reported as an SAE if it meets the criteria. Infusion reactions should be graded according to NCI CTCAE (Version 5.0) guidelines. All Grade 3 or 4 infusion reactions to cetuximab will be considered as DLT and will incur in immediate discontinuation of cetuximab treatment. Participants may continue to receive treatment with BMS-986315 upon discussion between investigator and the Sponsor.

Treatment recommendations are provided below and may be modified based on local treatment standards and guidelines, as appropriate.

For treatment with cetuximab, all recommendations described in [Section 7.4.2.2](#) apply. In addition:

- Premedicate with a histamine-1 (H1) receptor antagonist intravenously 30–60 minutes prior to the first dose or subsequent doses as deemed necessary
- For Grade 1 or 2 infusion reactions: interrupt the infusion and upon recovery, resume the infusion at 50% of the infusion rate.
- For Grade 3 or 4 infusion reactions: immediately and permanently discontinue cetuximab.

7.5 Preparation/Handling/Storage/Accountability

The investigational product should be stored in a secure area according to local regulations. It is the responsibility of the investigator to ensure that investigational product is only dispensed to study Participants. The investigational product must be dispensed only from official study sites by authorized personnel according to local regulations.

The product storage manager should ensure that the study treatment is stored in accordance with the environmental conditions (temperature, light, and humidity) as determined by BMS. If concerns regarding the quality or appearance of the study treatment arise, the study treatment should not be dispensed and contact BMS immediately.

Study treatment not supplied by BMS will be stored in accordance with the package insert.

Investigational product documentation (whether supplied by BMS or not) must be maintained that includes all processes required to ensure drug is accurately administered. This includes documentation of drug storage, administration and, as applicable, storage temperatures, reconstitution, and use of required processes (eg, required diluents, administration sets).

For study drugs not provided by BMS and obtained commercially by the site, storage should be in accordance with the product label.

Please refer to current version of the Investigator Brochures and/or pharmacy manual for complete preparation, storage, and handling information.

- Further guidance and information for final disposition of unused study treatment are provided in [Appendix 2](#) and the Pharmacy Manual.

7.5.1 *Retained Samples for Bioavailability / Bioequivalence / Biocomparability*

Not applicable.

7.6 Treatment Compliance

Study treatment compliance will be periodically monitored by drug accountability, as well as the participant's medical records and electronic case report form (eCRF). Study drug will be administered in the clinic by trained personnel. Drug accountability should be reviewed by the site study staff at each visit.

7.7 Concomitant Therapy

Concomitant medications are recorded at baseline and throughout study treatment and safety follow-up in the appropriate section of the eCRF.

All medications (prescription and over-the-counter [OTC]), vitamin and mineral supplements, and/or herbs taken by the participant from Screening through the Follow-up period will be documented and recorded, including start and stop date, dose and route of administration, frequency, and indication. Medications taken for a procedure (eg, biopsy) should also be included.

Any premedication use should be documented on the appropriate eCRF.

Anti-hypertensive medication usage should be documented on the appropriate eCRF. If anti-hypertensive medication is being periodically withheld, the exact dosing dates should be documented on the eCRF.

Prior anti-cancer treatments will be recorded during Screening and documented on the appropriate eCRF. Any subsequent anti-cancer therapy will be recorded until end of study or death, in the appropriate section of the eCRF.

Supportive medications for the management of acneiform rash for participants in Part 1C, as described in [Section 7.4.2.1](#), should be documented on the appropriate eCRF.

7.7.1 Prohibited and/or Restricted Treatments

The following medications are prohibited during the study (unless utilized to treat a drug-related AE):

- Any live/attenuated vaccine (eg, varicella, zoster, yellow fever, rotavirus, oral polio, and measles, mumps, rubella [MMR]) during treatment and until 100 days post last dose.
- Immunosuppressive agents
- Immunosuppressive doses of systemic corticosteroids (except as stated in [Section 6](#))
- Any concurrent anti-neoplastic therapy (ie, chemotherapy, hormonal therapy, immunotherapy, extensive, non-palliative radiation therapy)
- Any botanical preparation (eg, herbal supplements or traditional Chinese medicines) intended to treat the disease under study or provide supportive care. Use of marijuana and its derivatives for treatment of symptoms related to cancer or cancer treatment are permitted if obtained by medical prescription or if its use (even without a medical prescription) has been legalized locally.
- Administration of investigational SARS-CoV-2 vaccines is not allowed during the study. Participants may receive approved SARS-CoV-2 vaccines while continuing on study treatment at the discretion of the Investigator.
- Treatment of active SARS-CoV-2 infections or high-risk exposures, including use of investigational therapies, is allowed and should be discussed with the medical monitor.

No concomitant medications (prescription, over-the-counter, or herbal) are to be administered during study unless they are prescribed for treatment of specific clinical events. Any concomitant therapies must be recorded on the CRF.

7.7.2 Other Restrictions and Precautions

Participants with a condition requiring systemic treatment with either corticosteroids (> 10 mg daily prednisone equivalent) or other immunosuppressive medications within 14 days of treatment assignment are excluded. Inhaled or topical steroids, and adrenal replacement steroid doses > 10 mg daily prednisone equivalent, are permitted in the absence of active autoimmune disease.

For participants who need to undergo elective surgery (not tumor-related) during the study, it is recommended to hold study drug(s) for at least 2 weeks before and 2 weeks after surgery, or until

the participant recovers from the procedure, whichever is longer. Prior to resuming study drug treatment, surgically-related AEs should resolve to \leq Grade 1 or baseline and participant must meet relevant eligibility criteria as determined by the BMS Medical Monitor in discussion with the Investigator. The BMS Medical Monitor must be consulted prior to re-initiating treatment in a participant with a dosing interruption lasting > 8 weeks after the last dose.

7.7.2.1 Imaging Restriction and Precautions

It is the local imaging facility's responsibility to determine, based on participant attributes (eg, allergy history, diabetic history, and renal status), the appropriate imaging modality and contrast regimen per imaging study. Imaging contraindications and contrast risks are to be considered in this assessment. Participants with renal insufficiency are to be assessed as to whether or not they should receive contrast and if so, which contrast agent and dose is appropriate. Specific to MRI, participants with severe renal insufficiency (ie, estimated glomerular filtration rate (eGFR) < 30 mL/min/1.73 m²) are at increased risk of nephrogenic systemic fibrosis, therefore MRI contrast is contraindicated. In addition, participants may be excluded from MRI if they have tattoos, metallic implants, pacemakers, etc. This will be outlined in the image acquisition manual.

Gentle hydration before and after IV contrast should follow local standard of care. The ultimate decision to perform MRI in an individual participant in this study rests with the site radiologist, the investigator, and standards set by the local Ethics Committee.

7.7.3 Permitted Therapy

Participants are permitted the use of:

- Topical, ocular, intra-articular, intranasal, and inhalational corticosteroids (with minimal systemic absorption).
- Adrenal replacement steroid doses > 10 mg daily prednisone are permitted.
- A brief (less than 1 week) course of corticosteroids for prophylaxis (eg, contrast dye allergy) or for treatment of non-autoimmune conditions (eg, delayed-type hypersensitivity reaction caused by a contact allergen) is permitted.
- Supportive therapy for the management of acneiform rash as described in [Section 7.4.2.1](#).

7.7.3.1 Radiotherapy

Palliative and supportive care for disease-related symptoms may be offered to all participants on the trial; however, Investigators should consult with the BMS Medical Monitor prior to initiating palliative radiation in participants who have not yet completed the DLT evaluation interval (Parts 1A, 1B, and 1C).

The potential for overlapping toxicities with radiotherapy and BMS-986315 administered as monotherapy or in combination with nivolumab or cetuximab is currently not known. Therefore, palliative radiotherapy is not recommended while receiving any of these drugs, alone or in combination. If palliative radiotherapy in short courses and for isolated fields is required to control symptoms not clearly related to disease progression, then drug administration should be withheld,

if possible, for at least 1 week before radiation and for at least 1 week after its completion. Participants should be closely monitored for any potential toxicity during and after receiving radiotherapy. Prior to resuming study drug treatment, radiotherapy-related AEs should resolve to \leq Grade 1 or baseline and participants must meet relevant eligibility criteria as determined by the BMS Medical Monitor in discussion with the Investigator. The BMS Medical Monitor must be consulted prior to re-initiating treatment in a participant with a dosing interruption lasting > 8 weeks after the last dose.

Details of palliative radiotherapy should be documented in the source records and eCRF. Details in the source records should include: dates of treatment, anatomical site, dose administered and fractionation schedule, and AEs. Symptoms requiring palliative radiotherapy should be evaluated for objective evidence of disease progression. Participants receiving palliative radiation of target lesions will have the evaluation of BOR just prior to radiotherapy but such participants will no longer be evaluable for determination of response subsequent to the date palliative radiation occurs.

7.8 Treatment After the End of the Study

At the conclusion of the study, participants who continue to demonstrate clinical benefit will be eligible to receive BMS supplied study treatment up to the maximum duration of 26 cycles. Study treatment will be provided via an extension of the study, a rollover study requiring approval by responsible health authority and ethics committee or through another mechanism at the discretion of BMS.

BMS reserves the right to terminate access to BMS supplied study treatment if any of the following occur: a) The study is terminated due to safety concerns; b) The development of BMS-986315 is terminated for other reasons, including but not limited to lack of efficacy and/or not meeting the study objectives; c) The participant can obtain medication from a government sponsored or private health program. In all cases BMS will follow local regulations.

8 DISCONTINUATION CRITERIA

8.1 Discontinuation from Study Treatment

Participants MUST discontinue investigational product (and non-investigational product at the discretion of the investigator) permanently for any of the following reasons:

- Participant's request to stop study treatment. Participants who request to discontinue study treatment will remain in the study and must continue to be followed for protocol specified follow-up procedures. The only exception to this is when a participant specifically withdraws consent for any further contact with him/her or persons previously authorized by participant to provide this information
- Any clinical AE, laboratory abnormality or intercurrent illness which, in the opinion of the investigator, indicates that continued participation in the study is not in the best interest of the participant
- Documented disease progression as defined by RECIST v1.1 ([Appendix 7](#)) unless participants meet criteria for treatment beyond progression ([Section 5.1.5](#)).

- Clinical deterioration while receiving active study therapy that, in the opinion of the Investigator, indicates that continued participation in the study is not in the best interest of the participant.
- Any drug-related AE occurring at any time that meets DLT criteria as outlined in [Section 5.1.3](#) will require permanent discontinuation.
- Inability to comply with protocol.
- Discretion of the investigator.
- Pregnancy.
- Termination of the study by Bristol Myers Squibb (BMS)
- Loss of ability to freely provide consent through imprisonment or involuntarily incarceration for treatment of either a psychiatric or physical (eg, infectious disease) illness. (Note: Under specific circumstances and only in countries where local regulations permit, a participant who has been imprisoned may be permitted to continue as a participant. Strict conditions apply and BMS approval is required.)
- Individual participants with confirmed CR will be given the option to discontinue study therapy on a case by case basis after specific consultation and agreement between the investigator and BMS Medical Monitor in settings where benefit/risk justifies discontinuation of study therapy.
- Any event that leads to delay in dosing lasting > 8 weeks from the previous dose requires discontinuation, with the following exceptions:
 - Dosing delays to allow for prolonged steroid tapers to manage drug-related adverse events are allowed.
 - Dosing delays that occur for non-drug-related reasons may be allowed if approved by the BMS Medical Monitor (or designee).

Prior to re-initiating treatment in a participant with a dosing delay lasting > 8 weeks, the BMS Medical Monitor (or designee) must be consulted. Tumor assessments should continue as per protocol even if dosing is delayed. Periodic study visits to assess safety and laboratory studies should also continue every 6 weeks or more frequently if clinically indicated during such dosing delays.

Any adverse event, laboratory abnormality, or intercurrent illness which, in the judgment of the Investigator, presents a substantial clinical risk to the participant with continued nivolumab dosing.

The assessment for discontinuation of nivolumab should be made separately from the assessment made for discontinuation of BMS-986315. Although there is overlap among the discontinuation criteria, if a participant in any of the combination arms meets criteria for discontinuation and investigator is unable to determine whether the event is related to both or 1 study drug, the participant should discontinue both nivolumab and BMS-986315 and be taken off the treatment phase of the study. An exception to the discontinuation of BMS-986315 can be made in the case of a nivolumab-related hypersensitivity or infusion reaction.

Specifically for hypersensitivity or infusion related reactions, because nivolumab or cetuximab are administered first, if a participant presents with a reaction before the administration of

BMS-986315 has started, treatment with BMS-986315 may continue after the hypersensitivity or infusion related reactions have been resolved. For other immune-mediated AEs, when signs or symptoms have developed after administration of both study drugs, if discontinuation criteria are met, both study drugs should be discontinued. Refer to the Schedule of Activities for data to be collected at the time of treatment discontinuation and follow-up and for any further evaluations that can be completed.

In the case of pregnancy, the investigator must immediately, within 24 hours of awareness of the pregnancy, notify the BMS Medical Monitor/designee of this event. In the event a female participant becomes pregnant during a clinical trial, the study treatment must be discontinued immediately. If the investigator determines a possible favorable benefit/risk ratio that warrants continuation of study treatment, a discussion between the investigator and the BMS Medical monitor/designee must occur. In the event a partner of a male participant becomes pregnant, the investigator must immediately notify the BMS Medical Monitor/designee of this event. Refer to [Section 9.2.5](#) Pregnancy.

All participants who discontinue study treatment should comply with protocol specified follow-up procedures as outlined in [Section 2](#). The only exception to this requirement is when a participant withdraws consent for all study procedures including post-treatment study follow-up or loses the ability to consent freely (ie, is imprisoned or involuntarily incarcerated for the treatment of either a psychiatric or physical illness).

If study treatment is discontinued prior to the participant's completion of the study, the reason for the discontinuation must be documented in the participant's medical records and entered on the appropriate case report form (CRF) page.

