5.1.3 Dose Limiting Toxicities

For the purpose of guiding decisions regarding dose escalation in Parts 1A, 1B, and 1C, DLTs will be defined based on the incidence, intensity, and duration of AEs excluding toxicities clearly related to disease progression or intercurrent illness. The DLT period will start on the first day of cycle 1 and end at day 28 (therefore, 4 weeks) in Parts 1A, 1B and 1C. The severity of AEs will be graded according to National Cancer Institute (NCI) Common Terminology Criteria for Adverse Events (CTCAE) v5.0.

For the purpose of participant management, DLTs that occur at any time during treatment (not limited to DLT observation period) will result in study drug being held pending evaluation of the event being related to study drug, in accordance with [Section 7.4](#). A participant is considered DLT evaluable if receiving 1 dose of BMS-986315 in Part 1A, 1 dose of BMS-986315 and nivolumab (480mg) in Part 1B, or 1 dose of BMS-986315 and cetuximab (500 mg/m²) in Part 1C, and completing the DLT observation period.

Participants who withdraw from the study during the 4 week DLT evaluation period for reasons other than a DLT may be replaced with a new participant at the same dose level. The incidence of DLT(s) during the 4 week DLT evaluation period will be used in dose escalation decisions and to define the MTD/RP2D in monotherapy and in combination with nivolumab or cetuximab. AEs occurring after the 4-week DLT period will be considered for the purposes of defining the RP2D upon agreement between the Sponsor and Investigators. Participants experiencing a DLT will not be retreated with study drug (except for Grade 3 or 4 acneiform rash in Part 1C), and will enter the safety follow-up period of the study.

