5.1.3.5 Dose Limiting Toxicities Specific to Part 1C

In addition to all DLTs described in [Sections 5.1.3.1, 5.1.3.2, 5.1.3.3](#), and [5.1.3.4](#), in Part 1C the following adverse events will be considered DLTs:

- Grade 3 or 4 infusion reaction of any duration
- Grade 4 cetuximab-related rash
- Grade 3 cetuximab-related rash that does not improve by at least 1 Grade in \leq 2 weeks despite interruption of study therapy and maximal medical intervention.
- Please refer to [Section 7.4.2.1](#) for management of cetuximab-induced acneiform rash.

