7 TREATMENT

Study treatment is defined as any investigational treatment(s), marketed product(s), placebo or medical device intended to be administered to a study participant according to the study randomization or treatment allocation

Study treatment includes both Investigational [Medicinal] Product (IP/IMP) and Non-investigational [Medicinal] Product (Non-IP/Non-IMP) and can consist of the following:

- BMS-986315
- Nivolumab
- Cetuximab

An investigational product, also known as investigational medicinal product in some regions, is defined a pharmaceutical form of an active substance or placebo being tested or used as a reference in a clinical study, including products already with a marketing authorization but used or assembled (formulated or packaged) differently than the authorized form, or used for an unauthorized indication, or when used to gain further information about the authorized form.

Drugs used in this open-label study qualify as IPs. Their description and storage information are described in [Table 7-1](#). Please refer to the Pharmacy Manual for additional information.

Table 7-1: Study treatments for CA047004

Product Description / Class and Dosage Form	Potency	IP/Non-IMP	Blinded or Open Label	Packaging / Appearance	Storage Conditions (per label)
BMS-986315	120mg/mL	IP	Open Label	Kit	Refer to Product Label
Nivolumab	10 mg/mL	IP	Open Label	Kit	Refer to Product Label
Cetuximab	100 mg/50mL, 200 mg/100 mL & various strengths	IP	Open Label	Kit	Refer to Product Label

Abbreviations: IP: Investigational Product

Other medications used as support or escape medication for preventative, diagnostic, or therapeutic reasons, as components of the standard of care for a given diagnosis, may be considered as non-investigational products.

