 - Prior to re-initiating on-study treatment in a participant with a dosing delay lasting 8 weeks due to SARS-CoV-2 infection, the medical monitor/designee must be consulted

Participants with drug-related endocrinopathies adequately controlled with only physiologic hormone replacement may resume treatment after consultation with the BMS Medical Monitor (or designee).

7.4.2.1 *Management of Cetuximab-Induced Acneiform Rash*

Participants with SCCHN in Part 1C must have treatment withheld if diagnosed with Grade 3 or 4 dermatologic toxicity or acneiform rash. Treatment may be resumed when the event has improved to Grade 2, with dose management as described below. If Grade ≥ 3 rash does not resolve to Grade ≤ 2 within 14 days of interruption of cetuximab treatment and despite optimal supportive care, the patient should not receive any further treatment with cetuximab. BMS-986315 treatment may be continued upon discussion between the investigator and the sponsor.

The recommendations for management are as follows:

General/Prevention:

- Grade 1 rash: mild rash may not need treatment. However, if treatment is considered necessary, topical hydrocortisone (1% or 2.5%) cream and/or clindamycin 1% gel can be used.
- Grade 2 rash: relief from major symptoms caused by Grade 2 skin-related adverse events should be achieved by a combination of local and systemic therapies including systemic antibiotics (e.g., doxycycline or minocycline), topical treatment (e.g., hydrocortisone 2.5% cream, clindamycin 1% gel, pimecrolimus 1% cream), antihistamines (e.g., diphenhydramine). Oral corticosteroids will not be allowed for the management of Grade 1 and 2 rash.
- Grade 3 (or greater) rash: may be treated in a manner similar to Grade 2 rash. In the event of Grade ≥ 3 rash, treatment with cetuximab should be paused until recovery Grade ≤ 2 . Treatment should be resumed at a reduced dose (see below). If Grade ≥ 3 rash does not resolve to Grade ≤ 2 within 14 days of stopping cetuximab treatment and despite optimal supportive care, the patient should not receive any further treatment with cetuximab.

Grade 3 or 4 dermatologic toxicities and infectious sequelae (e.g., acneiform rash, mucocutaneous disease etc):

- 1st occurrence, Grade 3/4: delay infusion 1 to 2 weeks; if condition improves, continue at 500mg/m² Q2W. If no improvement, discontinue cetuximab.

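### In Part 1C, Section 8.1 requires permanent discontinuation for DLT-level rash that Sections 5.1.3 and 7.4.2.1 let participants be treated through, and 5.1.3 and 7.4.2.3 disagree on BMS-986315 after a Grade 3/4 cetuximab infusion reaction

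*Combined protocol and SAP*

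**What the plan says.** Section 8.1 opens its list with "Participants MUST discontinue investigational product (and non-investigational product at the discretion of the investigator) permanently for any of the following reasons". One bullet in that list is "Any drug-related AE occurring at any time that meets DLT criteria as outlined in" Section 5.1.3. Section 7 states "Drugs used in this open-label study qualify as IPs", so the list reaches BMS-986315, nivolumab and cetuximab alike. Further down, 8.1 adds a paragraph on infusion reactions: because the partner antibody is given first, BMS-986315 may go on once a reaction that began before its own infusion has resolved.

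Section 5.1.3 says "Participants experiencing a DLT will not be retreated with study drug (except for Grade 3 or 4 acneiform rash in Part 1C"). Other participants with a DLT move to safety follow-up.

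Section 5.1.3.5 adds DLTs for Part 1C: "Grade 3 or 4 infusion reaction of any duration", "Grade 4 cetuximab-related rash", and Grade 3 cetuximab-related rash that fails to improve by at least one grade within 2 weeks.

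Section 7.4.2.1, on Grade 3 or 4 rash in Part 1C, says "Treatment may be resumed when the event has improved to Grade 2, with dose management as described below". Its stepwise scheme allows cetuximab again after each of the first three Grade 3/4 occurrences if there is improvement. If a rash of Grade 3 or higher has not settled within 14 days, cetuximab ends but BMS-986315 may continue after discussion with the sponsor.

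Section 7.4.2.3 classes every Grade 3 or 4 cetuximab infusion reaction as a DLT that ends cetuximab, then adds "Participants may continue to receive treatment with BMS-986315 upon discussion between investigator and the Sponsor".

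Table 4-1 includes adverse events leading to discontinuation in the primary endpoint. Neither it nor Table 10.3.2-1 says which drug's discontinuation is meant.

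**The concern.** These are mandatory treatment rules, and for certain Part 1C events they cannot all be followed. Section 9 allows no protocol waivers, so a site that obeys one section departs from another. Two participants with the same event could be managed differently at two sites, with different exposure to BMS-986315 and different on-drug follow-up for safety and efficacy.

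The statistical consequence lies in the primary endpoint. Whether an event counts as leading to discontinuation may depend on which section the site read, rather than on the event.

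**Working it through.** No sample size, power or boundary figure in the plan depends on this point, so there is none to reproduce. The check sets the sections side by side for each type of Part 1C event.

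| Event in Part 1C | DLT? | 5.1.3 | 7.4.2.1 or 7.4.2.3 | 8.1 | Conflict |
|---|---|---|---|---|---|
| A. Grade 4 acneiform rash that improves | Yes | Retreatment allowed | Treatment may resume | Permanent stop | 8.1 against the other two |
| B. Rash of Grade 3 or higher, unresolved at 2 weeks | Yes | Retreatment allowed (acneiform) | Cetuximab ends; BMS-986315 may continue | Permanent stop | 8.1 against the other two, on BMS-986315 |
| C. Grade 3 rash that improves within 2 weeks | No | Not engaged | Treatment may resume | DLT bullet not triggered | None |
| D. Grade 3/4 cetuximab infusion reaction before BMS-986315 starts | Yes | No retreatment | Cetuximab ends; BMS-986315 may continue | Later paragraph lets BMS-986315 continue | 5.1.3 against the other two |
| E. Grade 3/4 cetuximab infusion reaction outside that timing | Yes | No retreatment | Cetuximab ends; BMS-986315 may continue | Permanent stop | 7.4.2.3 against the other two |

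Row E covers reactions after BMS-986315 has started. Day 15 visits, where Table 2-2 schedules cetuximab without BMS-986315, are not clearly addressed by the paragraph in 8.1.

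**Effect on the endpoint.** In row A, 8.1 produces a discontinuation and 5.1.3 with 7.4.2.1 does not, so the count differs however the term is defined. In rows B, D and E cetuximab stops under every section. The count there changes only if discontinuation means BMS-986315, or all study treatment.

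**Effect on dose finding.** Rows A, B, D and E are DLTs under every section, and row C is not a DLT under 5.1.3.5. The DLT counts entering the TITE-BOIN table are the same whichever section a site follows.

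**Scale.** Inputs are the Part 1C maximum in Section 10.1, 36 + 40 + 40 = 116, and the Grade 3/4 cetuximab rates in Section 3.2.3. Expected count = 116 × rate; the chance of at least one event = 1 − (1 − rate)^116.

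- Infusion reactions, 2% to 5%: 116 × 0.02 = 2.3 and 116 × 0.05 = 5.8. Chance of at least one: 0.90 to 0.997. The 2.2% quoted in 7.4.2.3 lies within this range (116 × 0.022 = 2.6).
- Dermatologic toxicity, 1% to 17%: 116 × 0.01 = 1.2 and 116 × 0.17 = 19.7. Chance of at least one: 0.69 to nearly 1.

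These are upper bounds on affected cases. The dermatologic range includes row C, which is not in conflict, and the documents give neither the Grade 4 share nor the unresolved Grade 3 share. The infusion range includes row D, where 8.1 and 7.4.2.3 agree.

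**The case against.** The strongest reply is that the text already resolves much of this. Section 7.4.1 applies the resumption criteria to participants who do not meet the permanent-discontinuation rules, and 7.4.2 opens with events that are not DLTs, so 7.4.2.1 might be read as covering only sub-DLT rash. That reading fails: 7.4.2.1 names Grade 4, and 5.1.3 expressly exempts Grade 4 acneiform rash from its rule for participants who have had a DLT. Nor does the cross-reference from 8.1 to 5.1.3 bring the exemption across, since it imports the DLT criteria only.

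For infusion reactions the reply is largely right as far as 8.1 is concerned. A reader might infer that 8.1 forbids BMS-986315 after every such reaction; its own later paragraph says otherwise. Section 5.1.2 puts a 60-minute observation period between cetuximab and BMS-986315, and 7.4.2.3 says about 90% of severe cetuximab reactions occur at the first infusion. If all of those appear before BMS-986315 starts, which is an assumption, about 10% fall outside the exception: 0.10 × 2.3 = 0.2 to 0.10 × 5.8 = 0.6 participants. This does not repair the mismatch between 5.1.3 and 7.4.2.3.

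A reader might also infer three competing rules for one event. The documents do not show that. For acneiform rash, 5.1.3 and 7.4.2.1 agree; for infusion reactions, 5.1.3 sides with the strict bullet of 8.1.

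Finally, Section 10.3 defers analysis detail to a later SAP, and 8.1 already requires the reason for discontinuation on the case report form. The SAP could define the endpoint term, but it cannot reconcile treatment rules that sites must follow during the trial.

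**Conclusion.** The contradiction stands in two places: DLT-level acneiform rash, where 8.1 opposes 5.1.3 and 7.4.2.1; and Grade 3/4 cetuximab infusion reactions, where 7.4.2.3 opposes 5.1.3 and, only outside the timing exception, 8.1. It affects participant management in Part 1C and can change one component of the primary endpoint, most clearly for a Grade 4 acneiform rash that improves.

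It would be tempting to read about 2 to 6 infusion reactions and 1 to 20 rashes as participants whose discontinuation status is in doubt. The documents do not support that. These counts apply general cetuximab rates to full Part 1C enrolment, although Section 6.2 excludes prior Grade 3/4 cetuximab infusion reactions, alpha-gal allergy and active severe acne or skin infection, and they include events that raise no conflict. The affected number cannot be derived. Nor is there any effect on DLT counts or TITE-BOIN decisions.

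**What to change.** Reconcile Sections 5.1.3, 7.4.2.1, 7.4.2.3 and 8.1, including both the DLT bullet and the infusion-reaction paragraph of 8.1, so that each Part 1C DLT type has one rule for BMS-986315 and one for cetuximab, stated the same way throughout. Cover reactions after BMS-986315 has started and those at cetuximab-only visits. Which clinical rule applies is for the sponsor to decide.

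Then report adverse events leading to discontinuation by drug in the safety table (Table 10.3.2-1), following the reconciled rule, and state what the summary count means: any study drug, BMS-986315, or all study treatment.

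The cost is protocol wording and a per-drug discontinuation field in the safety table. Sample size and the escalation design do not change.
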